2.5.4 Windows for time points

For the safety assessment, the reference date for the derivation of relative days of events or findings will be the date of first IMP dose injection in LTS12551 study. Selected safety variables will be summarized by the analysis window defined in Table 5 for the by-visit descriptive analysis. For all laboratory/vital sign/ECG variables, the summary statistics over visits for either measurements or mean change from baseline, and the plot of mean change from baseline over visits should use the centralized data only (if applicable), and should include the measurements obtained at either scheduled or unscheduled visits. For PCSA analyses, the measurements of laboratory/vital sign/ECG variables obtained at either scheduled visits or unscheduled visits should be used; and, both the centralized and local test results should be used (if applicable), as long as their available dates/time are different from each other's. All available safety measurements (from either scheduled or unscheduled visit) will be assigned to the appropriate visit window. In the event of multiple measurements of the same test in the same window, the one closest to the targeted visit date will be used for the by-visit summary. If they are at the same distance to the target day, the latest one will be used.

The pre-dose measurements at Week 0 of LTS12551 are defined as follows: for patients enrolled from DRI12544, the measurements at Week 0 are obtained from the EOS visit of DRI12544 if available, regardless whether the EOS visit in DRI12544 was combined with Visit 1/Visit 2 in LTS12551; otherwise, Week 0 value will be the last available measurement prior to the first IMP dose in LTS12551 study. For patients enrolled from EFC13579, EFC13691 and PDY14192, the measurements at Week 0 are obtained from the EOT visit of parent studies if available; otherwise, Week 0 value will be the last available measurement prior to the first IMP dose in LTS12551 study.

		Target	Vital	Signs	EC	CG	Physical Ex Urine A	xamination, Analysis	Hematolo Cher	gy, Serum nistry
VISIL	VVEEK	day	Minimum days	Maximum days	Minimum days	Maximum days	Minimum days	Maximum days	Minimum days	Maximum days
1 & 2	0	Derived		Up to 1st IMP dose date/time						
3	2	15	After 1st IMP dose date/time	21						
4	4	29	22	35					After 1st IMP dose date/time	56
5	6	43	36	49						
6	8	57	50	63						
7	10	71	64	77						
8	12	85	78	98			After 1st IMP dose date/time	126	57	126
9	16	113	99	126						
10	20	141	127	154						
11	24	169	155	210	After 1st IMP dose date/time	252	127	252	127	252
12	36	253	211	294						
13	48	337	295	378	253	504	253	420	253	420
14	60	421	379	462						
15	72	505	463	546			421	546	421	588
16	84	589	547	630			547	630		
17 (EOT)	96	673	631	d*	505	d*	631	d*	589	d*
18 (EOS)	108	757	d*+1		d*+1		d*+1		d*+1	

Table 5 - Time window for safety variables

*Note: d= max (last IMP dose +14 days, EOT date)

Statistical Analysis Plan SAR231893-LTS12551 - dupilumab

20-Jul-2017 Version number: 3

Vicit	Wook	Target day	Pregnar	ncy Test	Serum Immunoglobulin		
VISIL	Week	Taiget day	Minimum days	Maximum days	Minimum days	Maximum days	
1 & 2	0	Derived		Up to 1st IMP dose date/time		Up to 1st IMP dose date/time	
3	2	15					
4	4	29	After 1st IMP dose date/time	35			
5	6	43	36	49			
6	8	57	50	63			
7	10	71	64	77			
8	12	85	78	98			
9	16	113	99	126			
10	20	141	127	154			
11	24	169	155	210	After 1st IMP dose date/time	252	
12	36	253	211	294			
13	48	337	295	378	253	462	
14	60	421	379	462			
15	72	505	463	546			
16	84	589	547	630	463	630	
17 (EOT)	96	673	631	d*	631		
18 (EOS)	108	757	d*+1				

*Note: d= max (last IMP dose +14 days, EOT date)

For the efficacy assessment, the reference date for the derivation of relative days of events or findings will be the day of the first IMP injection in LTS12551 study. And for the endpoints not measured daily, all available values of scheduled measurements will be assigned to the appropriate visit window according to Table 6. In the event of multiple measurements of the same test in the same window, the one closest to the targeted visit date will be used for the by-visit summary. If they are at the same distance to the target day, the latest one will be used. The pre-dose measurements at Week 0 of LTS12551 are defined in the same way as in the paragraph prior to Table 5.

Vioit	Wook	Spirometry		ACQ-5, AQLQ		
		Target day	Minimum days Maximum days		Minimum days	Maximum days
1&2	0	Derived		1 st IMP dose date/time (Day 1)		1 st IMP dose date/time (Day 1)
3	2	15	2	21		
4	4	29	22	42		
5	6	43				
6	8	57	43	70		
7	10	71				
8	12	85	71	126		
9	16	113				
10	20	141				
11	24	169	127	252	2	252
12	36	253				
13	48	337	253	420	253	
14	60	421				
15	72	505	421	546		
16	84	589	547	630		
17 (EOT)	96	673	631	d*		
18 (EOS)	108	757	d*+1			

Table 6 - Time window for efficacy variables

*Note: d= max (last dose +14 days, EOT date)

Visit Week Target day		EQ-5D, R	esource Utilization	Prescribed	Prescribed OCS dose		
		Taiget day	Minimum days	Maximum days	Minimum days	Maximum days	
1&2	0	Derived		1 st IMP dose date/time (Day 1)		1 st IMP dose date/time (Day 1)	
3	2	15			2	21	
4	4	29			22	35	
5	6	43			36	49	
6	8	57			50	63	
7	10	71			64	77	
8	12	85	2	126	78	98	
9	16	113			99	126	
10	20	141			127	154	
11	24	169	127	252	155	210	
12	36	253			211	294	
13	48	337	253	420	295	378	
14	60	421			379	462	
15	72	505	421	546	463	546	
16	84	589	547	630	547	630	
17 (EOT)	96	673	631	d*	631	d*	
18 (EOS)	108	757	d*+1		d*+1		

*Note: d= max (last dose +14 days, EOT date)

For the pharmacokinetics/pharmacodynamics variables summary, the reference date for the derivation of relative days of measurements will be the date of first IMP dose injection in LTS12551 study. Pharmacodynamics variables will be summarized by the analysis window defined in Table 7 for the by visit descriptive analyses. All available values of scheduled measurements will be assigned to the appropriate visit window. In the event of multiple measurements of the same test in the same window, the one closest to the targeted visit date will be used for the by-visit summary. If they are at the same distance to the target day, the latest one will be used. The pre-dose measurements at Week 0 of LTS12551 are defined in the same way as in the paragraph prior to Table 5.

Vieit	Visit Week Target day		PK sampling, dupilu	imab concentration	Anti-drug antibodies		
VISIC			Minimum days	Maximum days	Minimum days	Maximum days	
1 & 2	0	Derived		Up to 1st IMP dose date/time		Up to 1st IMP dose date/time	
3	2	15					
4	4	29	After 1st IMP dose date/time	56			
5	6	43					
6	8	57					
7	10	71					
8	12	85	57	126	After 1st IMP dose date/time	126	
9	16	113					
10	20	141					
11	24	169	127	252	127	252	
12	36	253					
13	48	337	253	420	253	420	
14	60	421					
15	72	505	421	588	421	588	
16	84	589					
17 (EOT)	96	673	589	d*	589	d*	
18 (EOS)	108	757	d*+1		d*+1		

Table 7 - Time window for pharmacokinetics and pharmacodynamics variables

*Note: d= max (last dose +14 days, EOT date)

Visit	Week	Target	et Total IgE		
Viole	Hook	day	Minimum days	Maximum days	
1 & 2	0	Derived		Up to 1st IMP dose date/time	
3	2	15			
4	4	29			
5	6	43			
6	8	57			
7	10	71			
8	12	85			
9	16	113			
10	20	141			
11	24	169			
12	36	253			
13	48	337	After 1st IMP dose date/time	462	
14	60	421			
15	72	505			
16	84	589	463	630	
17 (EOT)	96	673	631		
18 (EOS)	108	757			

*Note: d= max (last dose +14 days, EOT date)

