9.2.1.4 Clinical laboratory tests

The clinical laboratory tests will be conducted by an accredited central laboratory with national and regional clinical licenses, as required for diagnostic testing, and must provide evidence of participation in proficiency testing, as appropriate. After reviewing the laboratory report and evaluating any results that are outside the normal range, the Investigator must sign and date the laboratory report. Abnormal laboratory values that are considered to be clinically significant by the Investigator must be repeated as soon as possible after receiving the laboratory report, to rule out laboratory error. Persistent abnormal laboratory values should be repeated until they return to normal or until an etiology of the persistent abnormality is determined.

The following laboratory tests will be performed (as per the schedule of assessments, see flow charts in [Section 1.2](#) and [Section 1.3](#)). Patients will be informed of fasting requirements for hematology and serum chemistry assessments.

- Hematology: Blood count (erythrocytes, hemoglobin, hematocrit, leukocytes), differential blood count (neutrophils, lymphocytes, monocytes, eosinophils, and basophils) and platelets.
- Serum chemistry: Total bilirubin (in case of values above the normal range, differentiation in conjugated and non-conjugated bilirubin), alanine aminotransferase (ALT), aspartate aminotransferase (AST), alkaline phosphatase (ALP), total protein, albumin, total cholesterol, creatine phosphokinase (CPK), glucose, creatinine, blood urea nitrogen (BUN), uric acid, bicarbonate, and electrolytes (sodium, potassium, and chloride).
- Urine analysis: pH, glucose, ketones, leukocyte esterase blood, protein, nitrate, urobilinogen, and bilirubin (by dipstick). If any parameter on the dipstick is abnormal, a urine sample should be sent to the central laboratory for testing. If positive for proteins, microscopic analysis is performed by central laboratory.
- Serum immunoglobulin, including IgE, are no longer to be assayed due to Amendment 04.

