2.5.5 Unscheduled visits

Unscheduled visit measurements of laboratory data, vital signs, and ECG will be included in the by-visit summaries and figures, as well as the computation of baseline, worst values, and PCSAs.

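### The End-of-Study row of SAP Table 5 has a fixed target of Day 757 and no upper limit, so in 48-week patients and early stoppers a later central retest can displace the scheduled End-of-Study safety value

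*SAP*

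**What the plan says.** Three rules in the SAP act together.

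- **Which values compete.** SAP 2.5.4: "All available safety measurements (from either scheduled or unscheduled visit) will be assigned to the appropriate visit window". By-visit statistics and mean-change plots "should use the centralized data only (if applicable), and should include the measurements obtained at either scheduled or unscheduled visits". SAP 2.5.5 repeats the point: "Unscheduled visit measurements of laboratory data, vital signs, and ECG will be included in the by-visit summaries and figures".
- **Which value is kept.** Within a window, "the one closest to the targeted visit date will be used for the by-visit summary". On ties: "If they are at the same distance to the target day, the latest one will be used".
- **The End-of-Study window.** Table 5 has one such row, "18 (EOS) 108 757 d*+1", with the maximum left blank. The note below the table defines "d= max (last IMP dose +14 days, EOT date"), so the start of the window follows the patient and the target does not.

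The protocol has more than one End-of-Study day. It is Week 108 for 96-week patients (10.1.1.17), Week 60 for 48-week patients (10.1.2.13), and 12 weeks after the End-of-Treatment assessment for those who stop early (10.3.4).

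On retesting, Protocol 9.2.1.4 requires clinically significant abnormal laboratory results to be repeated promptly to rule out laboratory error. It adds: "Persistent abnormal laboratory values should be repeated until they return to normal", or until the cause of the abnormality has been established.

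**The concern.** A closest-to-target rule works when the target is the planned visit day. For the End-of-Study row that is true only of 96-week completers. For patients whose End-of-Study visit falls well before Day 757, closest to target in practice means latest available, and the blank maximum sets no stop. Values from the post-study epoch, which SAP 2.1.4 separates from follow-up, can therefore enter the row and take it over.

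Later laboratory values are not a random sample. Under the repeat rule they arise mainly in patients whose End-of-Study result was abnormal, and some are taken because repetition continues until the value is normal. This row is the by-visit view of safety values after the end of the 12-week drug-free period. It would combine scheduled values from most patients with later retests from some. How readily a retest takes over would depend on the patient's actual End-of-Study day.

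**Working it through.** **Inputs.** Day 1 is the first LTS12551 dose (SAP 2.5.4). The End-of-Study target is Day 757, the minimum d+1 and the maximum blank (Table 5). End-of-Study weeks are from Protocol 10.1.1.17, 10.1.2.13 and 10.3.4. Visit tolerance after Week 12 is ±7 days (Protocol 1.2 and 1.3, footnote a).

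**Reproducing the plan's figure.** Target day = 7 × week + 1. Week 108 gives 757, Week 96 gives 673, Week 60 gives 421 and Week 48 gives 337, all as printed in Table 5.

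**Where a 48-week completer falls.** End-of-Treatment is Day 337, so d = 337 and the End-of-Study window opens on Day 338. The planned visit is 337 + 84 = Day 421. The target remains Day 757.

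**Comparison of two patients, each retested 14 days later.**

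- 48-week completer: |421 - 757| = 336 and |435 - 757| = 322. The retest is kept.
- 96-week completer: |757 - 757| = 0 and |771 - 757| = 14. The scheduled value is kept.

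**General bound.** Let the scheduled value fall on Day E < 757 and a later one on Day R. If R ≤ 757, R is closer and wins. If R > 757, R wins when R - 757 ≤ 757 - E, that is, R ≤ 1514 - E. Equality counts because ties go to the later value.

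| Patient | E | Displaced through Day 1514 - E | Days after E |
|---|---|---|---|
| End-of-Treatment at Week 24 | 253 | 1261 | 1008 |
| 48-week completer | 421 | 1093 | 672 |
| End-of-Treatment at Week 72 | 589 | 925 | 336 |
| End-of-Treatment at Week 84 | 673 | 841 | 168 |
| End-of-Treatment at Week 92 | 729 | 785 | 56 |
| 96-week completer, visit 7 days early | 750 | 764 | 14 |
| 96-week completer, visit on target | 757 | none | 0 |

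**Across the visit tolerance.** For End-of-Study on Days 414 to 428 (48-week patients), a retest 7, 14 or 21 days later wins on 15 of 15 possible visit days. For Days 750 to 764 (96-week completers) it wins on 4, 1 and 0 of 15.

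**With a patient-specific target.** d + 84 is 337 + 84 = 421 for a 48-week completer and 673 + 84 = 757 for a 96-week completer, so the printed target is kept where it was right. The 48-week counts become 4, 1 and 0 of 15, the same as for 96-week completers. Preferring the scheduled value removes the rest.

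**Row assignment.** For a 48-week patient, Day 421 also lies in fixed rows of Table 5: vital signs Week 60 (379 to 462, target 421), haematology and chemistry Week 72 (421 to 588, target 505), and ECG Week 48 (253 to 504, target 337). The SAP states no precedence. If only the fixed rows applied, the scheduled vital-sign value would be kept (distance 0 against 14). A Day 435 chemistry retest would still win (|435 - 505| = 70 against |421 - 505| = 84).

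**The case against.** The strongest reply is that nothing happens unless a central value is recorded after the last planned visit. Without one, the rule normally returns the scheduled End-of-Study value. Local retests do not compete where central data apply, and the documents give no count of post-End-of-Study central retests. This stands: the mechanism is certain on the assumed row, and its frequency is unknown.

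A reader might infer more than the documents support:

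- **That vital signs and ECG are pulled toward normal too.** The repeat rule in Protocol 9.2.1.4 covers laboratory values. The ECG recheck in 9.2.1.3 and 10.3.3 precedes a decision to stop study drug, which does not arise after End-of-Study.
- **That the shift toward normal is established.** Repetition may also end once a cause is found, and the first repeat is there to detect laboratory error, so the replacing value may be the more accurate one. The direction is plausible, not shown.
- **That 96-week completers are immune and everyone else is exposed without limit.** A completer seen up to 7 days early can lose the scheduled value to a retest within about 14 days. A patient whose End-of-Treatment is at Week 92 is exposed for only 56 days. The driver is the actual End-of-Study day, not the planned duration.
- **That efficacy and pharmacokinetic tables share the fault.** The rules for Tables 6 and 7 assign scheduled measurements only.
- **That safety signals are lost.** Counts of potentially clinically significant abnormalities (PCSAs) use all scheduled and unscheduled values in the treatment-emergent period, which includes follow-up. Endpoint and worst values stop at last dose + 14 days. Patients with a laboratory PCSA are listed with the full profile of that biological function (SAP 2.4.5 and 2.4.5.3).

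The row overlap is also a fair objection. The d+1 start makes the End-of-Study row the natural home for post-treatment values, but the SAP does not say so.

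**Conclusion.** The point holds as a defect in a stated rule. Assuming values after d go to the End-of-Study row, a 48-week completer's scheduled safety value is displaced by any later central value through Day 1093 (Days 1086 to 1100 across the visit tolerance). An early stopper's value is displaced through Day 1514 - E. In 96-week completers, displacement by a later value requires an early visit and a quick retest.

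The consequence is small. It is limited to the End-of-Study row of descriptive by-visit safety summaries and plots, and matters mainly for laboratory parameters, where abnormal results are the ones retested. The primary endpoint, PCSA counts, and endpoint and worst values are unaffected. The size cannot be calculated from the documents. This is a minor point, worth correcting because it is nearly free.

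**What to change.** Add a footnote to Table 5 only:

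1. The End-of-Study target is d + 84 days for each patient.
2. The window runs from d+1 to d + 91, the end of the 12-week follow-up plus the 1-week visit allowance. This brings it close to the follow-up and post-study epochs of SAP 2.1.4.
3. The scheduled End-of-Study measurement is used when available; the closest-to-target rule applies only when it is missing.
4. Values after d go to the End-of-Study row and not to the overlapping fixed rows.

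The cost is the footnote and a small programming change. No new data are needed, and retests remain available for the PCSA analyses and listings.

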10.1.2.11 Visit 12 (Month 9, Week 36)

- Record all medication use with start dose in e-CRF including starting dose.
- Inquire about AEs/SAEs and background asthma therapy tolerability.
- Measure vital signs (blood pressure, heart rate, respiration rate, body temperature, weight).
- Perform urine pregnancy test (for women of childbearing potential).
- Call IVRS/IWRS to register visit and obtain treatment kits' numbers.
- Dispense and administer IMP:

- Patients will be monitored at the study site for a minimum of 30 minutes after the injection.
- After Week 12, for patients (or parents caregivers) unable or unwilling to self-administer IMP, arrangements must be made for the patient to receive IMP injections at the study site as unscheduled visits, or for qualified site personnel and/or a professional caregiver to administer IMP at home at q2w intervals.
- Remind patient to continue the background therapy.
- Schedule appointment for next visit and remind patient to withhold the last dose of salbutamol/albuterol or levosalbutamol/levalbuterol for at least 6 hours and withholding the last dose of LABA for at least 12 hours (ultra-LABA like vilanterol should be withheld for at least 24 hours) and withholding the last dose of LAMA for at least 24 hours prior to the next visit.
- Remind patients for the next visit in fasting state.
- Perform monthly telephone contact with patient after Week 24 (Visit 11) to collect safety information.

Note: Patient's next visit will be Visit 17 (EOT: Month 12, Week 48)

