2.1.3.2 Forced expiratory volume in one second (FEV1) and other spirometry assessments

The forced expiratory volume in one second (FEV1) is part of the spirometry assessment that will be performed at Visit 1, Visit 3 (Week 2), Visit 4 (Week 4), Visit 6 (Week 8), Visit 8 (Week 12), Visit 11 (Week 24), Visit 13 (Week 48; if applicable), Visit 15 (Week 72; if applicable), Visit 16 (Week 84; if applicable), Visit 17 (End-of-Treatment) and Visit 18 (End-of-Study). The other parts of the spirometry assessment, including the percent predicted FEV1, Forced Vital Capacity (FVC) and Forced Expiratory Flow (FEF) 25-75%, will be performed at the same visits as above.

A spirometer that meets the 2005 American Thoracic Society (ATS) / European Respiratory Society (ERS) recommendations will be used. The ATS/ ERS Standardization of Spirometry should be used as a guideline (1). Spirometry should be done at the study site approximately the same time of the day (preferably in the morning, but it could be done at a different time of the day). Spirometry will be performed after a washout period of bronchodilators according to their action duration (for example, withholding the last dose of salbutamol/albuterol or levosalbutamol/levalbuterol for at least 6 hours and withholding the last dose of LABA for at least 12 hours [ultra-LABA like vilanterol should be withheld for at least 24 hours] and withholding the last dose of LAMA for at least 24 hours). Also spirometry should be performed prior to IMP administration, as applicable.

Pulmonary function tests will be measured in the sitting position and the highest measure will be recorded in liters for FEV1.

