2.1.4.4 Vital signs variables

Vital signs, including blood pressure (mmHg), heart rate (beats per minute), respiratory rate (breaths per minute), body temperature (degrees Celsius) and body weight (kg) will be measured at every scheduled visit. Height (cm) will be measured at Visit 1 only. Vital signs will be measured in the sitting position using the same arm at each visit, and will be measured prior to receiving investigational product at the study visits. Baseline values for vital signs will be the original baseline from the parent studies.

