2.1.4.5 Electrocardiogram variables

ECG results will be from an independent central lab. Baseline values for ECG will be the original baseline from the parent study.

One recording of a standard 12-lead ECG will be performed at Visit 1, Visit 11 (Week 24), Visit 13 (Week 48; if applicable), Visit 17 (End-of-Treatment) and Visit 18 (End-of-Study). A minimum of 3 complexes in an appropriate lead (lead II) will be averaged to determine the PR-interval, QT/QTcF/QTcB interval, QRS-complex and heart rate will be measured for each ECG. At the post-enrollment visits, ECGs will be performed prior to investigational product administration. All ECGs will be performed with the subject in a reclined position.

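### SAP 2.5.4: the Week 2 to 84 windows are not cut at end of treatment, so an off-drug value can meet both a fixed-week row and the EOS row

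*SAP*

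**What the plan says.** SAP 2.5.4 places values in visit windows counted from the first LTS12551 dose. For efficacy, "all available values of scheduled measurements will be assigned to the appropriate visit window according to Table 6". For safety the net is wider: "All available safety measurements (from either scheduled or unscheduled visit) will be assigned to the appropriate visit window". SAP 2.5.5 repeats this: "Unscheduled visit measurements of laboratory data, vital signs, and ECG will be included in the by-visit summaries and figures". PK and pharmacodynamic values follow the efficacy wording.

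The footnote to Tables 6 and 7 reads "Note: d= max (last dose +14 days, EOT date"), and Table 5 has the same definition. In all three tables d appears in two places only: as the upper limit of the Visit 17 (EOT) row and, as d+1, the lower limit of the Visit 18 (EOS) row. Every row from Week 2 to Week 84 has plain numeric limits. There is one set of windows for both treatment lengths.

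The only conflict rule in 2.5.4 takes the value nearest the target day, and the later one on a tie, when several values fall in the same window. No rule covers one value that falls in two windows.

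The Protocol puts EOT 2 weeks after the last dose and EOS 12 weeks after EOT (10.1.2.12 and 10.1.2.13), with visit windows of ± 1 week after Week 12 (1.3, footnote a). After Visit 12 in the 48-week schedule, "Patient's next visit will be Visit 17 (EOT: Month 12, Week 48").

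**The concern.** A 48-week completer reaches EOS at about Week 60, and an early stopper reaches it about 12 weeks after EOT, whenever that was. By study day, these values lie inside windows built for patients still on drug in the 96-week schedule. They also lie inside the EOS row. Two programmers could follow 2.5.4 and produce different tables.

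A completer's EOS value is taken 2 + 12 = 14 weeks after the last dose. SAP 1.5 records that in DRI12544 the median concentration 12 weeks after the last dose of 300 mg q2w was below the limit of quantitation. If such values entered the Week 60 or Week 72 row, a row that reads as on-treatment would mix treated and washed-out patients. Concentrations there would look lower, and FEV1 and laboratory courses would be blurred in the tables meant to show long-term maintenance.

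**Working it through.** **1. Reproduce the printed windows.** Target day = 7 × week + 1 gives Week 48 = 337, Week 60 = 421, Week 96 = 673 and Week 108 = 757, as printed. Each fixed upper limit equals the midpoint to the next scheduled target in the 96-week schedule, minus 1. For spirometry at Week 48, (337 + 505)/2 − 1 = 420, as printed. The limits therefore come from the 96-week schedule alone.

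**2. 48-week completer.** EOT is on Day 337 ± 7 = 330–344. EOS is on Day 421 ± 7 = 414–428, which is 15 allowed days. With EOT on its target day, d = 337 and the EOS row is open from Day 338. Each EOS value also meets a fixed row:

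| Variable | Fixed row (days) | Allowed EOS days inside |
|---|---|---|
| Vital signs, pregnancy test, OCS dose | Week 60 (379–462) | 15 of 15 |
| Spirometry, physical examination, urinalysis, resource utilisation | Week 72 (421–546) | 8 of 15 (421–428) |
| Haematology and chemistry, PK, ADA | Week 72 (421–588) | 8 of 15 (421–428) |
| ECG | Week 48 (253–504) | 15 of 15 |

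For the two Week 72 groups, the other 7 days (414–420) meet the Week 48 row. In Week 48, including ECG, the EOT value is at most 7 days from target and the EOS value at least 414 − 337 = 77. The nearest-value rule then keeps EOT unless it is missing. The exposure is thus mainly in Weeks 60 and 72, where a 48-week patient has no on-treatment value.

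If EOS is timed from the actual EOT, it spans 330 + 84 − 7 = 407 to 344 + 84 + 7 = 435, or 29 days. Week 60 then contains 29 of 29 and Week 72 contains 15 of 29 (421–435).

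**3. Early stoppers: where the overlap ends.** With EOT on day d and EOS on d + 84, the EOS value meets a fixed row while d + 84 does not exceed the last fixed limit:
- vital signs, spirometry, physical examination, urinalysis, pregnancy test, resource utilisation and OCS dose: 630 − 84 = 546
- haematology and chemistry, PK, ADA: 588 − 84 = 504
- ECG: 504 − 84 = 420

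**4. Early stoppers: which row would select the EOS value.** This assumes that the fixed row is applied, visits fall on target days in the 96-week schedule, and the nearest value is taken (later on a tie), for d from 15 to 672.
- Spirometry and urinalysis: Week 12 for d = 15–42, Week 24 for 43–127, Week 48 for 169–295, Week 72 for 337–462, Week 84 for 463–546.
- Laboratory, PK and ADA: the same through Week 48, then Week 72 for 337–463.
- ECG: Week 24 for 15–127, Week 48 for 169–295.
- Vital signs: some row from Week 16 to Week 84 for every d from 15 to 546.

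**5. 96-week completer.** d is about 673 and EOS about 757. Every fixed row ends by Day 630, so there is no overlap.

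**6. After the fix.** With each fixed row ending at the smaller of its maximum and d, double matches fall to 0 for all ten groups of variables with an EOS row and for every d from 15 to 672. A 48-week completer's EOT value on Day 337 stays in Week 48.

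**The case against.** The best defence is that the intent is plain. The EOS row opens at a patient-specific d+1, which serves a purpose only if later values belong there. Rows carry visit numbers, and the 48-week flow chart goes from Visit 12 to 17 to 18, so its Week 60 is Visit 18. SAP 2.1.3.2 marks late visits as conditional: "Visit 15 (Week 72; if applicable), Visit 16 (Week 84; if applicable), Visit 17 (End-of-Treatment) and Visit 18 (End-of-Study"). The ECG list does the same: "Visit 13 (Week 48; if applicable), Visit 17 (End-of-Treatment) and Visit 18 (End-of-Study"). SAP 2.4.3.1 likewise notes that exposure categories beyond Week 48 may apply only to 96-week patients.

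Most of this stands, and EOS is the likely intent. It does not close the gap. The conditional labels are absent for vital signs, which "will be measured at every scheduled visit". They exempt 48-week patients from visits, but they do not remove an early stopper's value from a window. Visit numbers also cannot place the unscheduled laboratory, vital-sign and ECG values that the SAP puts into by-visit summaries.

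Three stronger readings are tempting and are not supported:
- A reader might infer that the SAP directs off-drug values into on-treatment rows. It does not. The same value also meets the EOS row, so the text leaves two candidates.
- A reader might infer that a 48-week patient's EOT value has no row. The EOT row is indeed empty for them, starting at Day 631 (589 for laboratory, PK and ADA; 505 for ECG). But Days 330–344 lie in the Week 48 row and no other.
- A reader might infer that safety conclusions are at risk. The TEAE and exacerbation analyses do not use these windows, and endpoint and worst values are tied to end of treatment (SAP 2.4.5).

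**Conclusion.** The point holds as a minor defect in printed rules. The windows overlap for values after d, and nothing in 2.5.4 decides between the two rows. Confidence is high that the overlap exists. Any effect on results depends on how the tables are programmed.

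The size is conditional. If the fixed row is applied, a 48-week completer's EOS value enters Week 60 on 15 of 15 allowed days for vital signs, and Week 72 on 8 of 15 for spirometry, urinalysis, laboratory, PK and ADA. The early-stopper ranges rest on the same reading and on visits on target days. They count days, not patients. The number of patients cannot be computed, because neither the 48/96-week split nor the dropout is given. Treating OCS dose as a visit value is an assumption, since the documents describe a prescribed dose recorded in the e-CRF. That part concerns EFC13691 patients only (210 randomised).

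The scope is the descriptive by-visit summaries of spirometry, OCS dose, resource utilisation, laboratory, vital signs, ECG, physical examination, urinalysis, pregnancy test, PK and ADA. ACQ-5 and AQLQ are not scheduled at EOS. DRI12544 enrolment was already complete at Amendment 04, so in those columns only early stoppers matter.

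**What to change.** State in SAP 2.5.4 that:
1. each Week 2 to 84 window ends at the smaller of its printed maximum and d;
2. any value after d, scheduled or unscheduled, goes only to one post-treatment (EOS) row, whatever the planned treatment length, with target EOT + 84 days in place of Day 757;
3. values up to d, including the EOT value of 48-week patients and early stoppers, stay in the fixed window that contains their study day, which is Week 48 for a 48-week completer.

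The cost is a few sentences and window programming, and slightly fewer values at some fixed weeks. For 96-week completers the fixed rows do not change. At most the new EOS target changes which of several values after d is chosen. For example, with EOT on Day 680, an unscheduled value on Day 755 and EOS on Day 764, the choice moves from Day 755 (2 days from 757) to Day 764 (the new target, 680 + 84).
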